12.3. Sample Size

The minimum required sample size to evaluate the primary endpoints and account for up to 20% attrition is 62 (Table 12-1).

Table 12-1: Endpoint Sample Size Estimates

Endpoint	Measurement	Hypotheses ¹	Expected Performance	Power	Number of Subjects	
					needed for analysis	to be enrolled for ≤ 20% attrition
Primary Safety Endpoint	DRCFR from 0 to 3 months	$H_0: \text{DRCFR} \leq 87.5\%$ $H_A: \text{DRCFR} > 87.5\%$	97.5%	80%	49	62
Primary Effectiveness Endpoint	LV pacing threshold at 3 months	$H_0: \text{mean} \geq 2.5\text{V}$ $H_A: \text{mean} < 2.5\text{V}$	$1.9 \pm 1.2\text{V}$	90%	36	45

¹ Hypothesis test based on a one-sided alpha level of 0.05.

LV=left ventricular; DRCFR=device-related complication free rate

Sample sizes were calculated employing exact binomial methods (primary safety endpoint) and one-sample t-test methodology (primary effectiveness endpoint) in nQuery 6.0.

The following assumptions were used for the calculation of sample sizes:

- Primary Safety Endpoint
 - Expected DRCFR = 97.5% (determined from prior comparable BSC devices)
 - Performance goal = 87.5% (clinically accepted delta of 10%, subtracted from expected DRCFR)
 - Test significance level (α) = 0.05 (one-sided)
 - Power = 80%
- Primary Effectiveness Endpoint
 - Expected mean (\pm standard deviation [SD]) LV pacing threshold = $1.9 \pm 1.2\text{V}$ (based on prior BSC LV lead performance)
 - Performance goal = 2.5V (used in prior BSC led approval studies)
 - Test significance level (α) = 0.05 (one-sided)
 - Power = 90%

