Statistical Test Method	
Sample Size Methodology:
 
 • Sample size for the primary safety endpoint was calculated using exact binomial methods for comparison of a single proportion to a performance goal. • Sample size for the primary effectiveness endpoint was calculated using one-sample t-test methodology for comparison of a single mean to a performance goal. 
Analysis Methods:
 
 • The DRCFR from implant will be calculated as the proportion of actively enrolled subjects without a device-related complication through 3 months after implant. The null hypothesis will be rejected and the endpoint considered met if the lower one-sided 95% confidence bound for the proportion of subjects with no device-related complication is greater than 87.5%. • Regarding mean LV pacing threshold at 3 months post-implant, the null hypothesis will be rejected and this endpoint considered met if the upper one-sided 95% confidence bound for the mean LV pacing threshold at 3-months is less than 2.5V. 
Further details on analytical methods can be found in Section 12.0 of the CIP.

Sample Size Parameters	
DRCFR through 3 months post-implant: 62 subjects. Sample size was calculated assuming a 97.5% DRCFR, a performance goal of 87.5%, one-sided alpha level of 0.05, 80% power, and 20% attrition.
 
Mean LV pacing threshold at 3 months post-implant: 45 subjects. Sample size was calculated assuming a mean (\pm standard deviation [SD]) LV pacing threshold of $1.9 \pm 1.2V$, a performance goal of 2.5V, one-sided alpha level of 0.05, 90% power, and 20% attrition.
 
Based on the above sample size calculations, the minimum required sample size to statistically power the primary endpoints is 62 subjects.

3. Table of Contents

1. TITLE PAGE	1
2. CLINICAL INVESTIGATION PLAN SYNOPSIS	4
3. TABLE OF CONTENTS.....	10
3.1. Table of Figures.....	13
3.2. Table of Tables	14
4. INTRODUCTION	15
5. DEVICE DESCRIPTION.....	18
5.1. Ingenio 2 Cardiac Resynchronization Therapy Pacemakers.....	18
5.1.1. PaceSafe.....	21
5.1.2. Post-Operative System Test.....	21
5.1.3. Atrial Arrhythmia Reports	22
5.1.4. ECG/EGM Snapshots	22
5.1.5. Leads.....	22
5.1.6. ZIP Telemetry	22
5.1.7. Programming System.....	22
5.2. Ingenio 2 CRT-P Indications for Use	23
5.3. Ingenio 2 CRT-P Contraindications.....	24
6. STUDY OBJECTIVE	24
7. ENDPOINTS	24
7.1. Primary Safety Endpoint.....	24
7.2. Primary Effectiveness Endpoint	24

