12.1.1.2. Statistical Methods

When the final study subject reaches the 3 Month required follow-up visit, the primary safety analysis will be performed based on exact binomial methods for the estimation of the DRCFR, including the exact lower one-sided 95% confidence bound. Subjects that die/withdraw or are lost-to-follow-up prior to the 3-month endpoint evaluation ($\leq 91 + 21$ days post-implant or post-implant attempt) and have not experienced device-related complications will be excluded from the analysis. The sample size was adjusted to account for up to 20% attrition to ensure there would be a sufficient number of evaluable subjects through 3-months.

The primary safety endpoint will evaluate the DRCFR through 3-months post-implant (or implant attempt), calculated using exact binomial methods. The null hypothesis will be rejected and the endpoint considered met if the lower one-sided 95% confidence bound for the DRCFR at 3-months is greater than 87.5%.

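### The safety sample size reproduces, but dropping only complication-free leavers biases the DRCFR downward, and 80% power holds only while no more than 12 or 13 of 62 subjects are lost

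*Combined protocol and SAP*

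**What the plan says.** Section 12.3 and Table 12-1 size the primary safety endpoint for a DRCFR of 97.5% against a goal of 87.5%. They give 49 subjects for analysis and 62 to enrol, with attrition written as a maximum: "The minimum required sample size to evaluate the primary endpoints and account for up to 20% attrition is 62". The synopsis (Sample Size Parameters) omits that qualifier: "Sample size was calculated assuming a 97.5% DRCFR, a performance goal of 87.5%, one-sided alpha level of 0.05, 80% power, and 20% attrition".

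Section 12.1.1.2 specifies exact binomial estimation, "including the exact lower one-sided 95% confidence bound", with success if that bound exceeds 87.5%. Subjects who die, withdraw or are lost before the 3-month evaluation and "have not experienced device-related complications will be excluded from the analysis". Section 12.4.1 repeats the rule.

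Section 12.4.1 also puts subjects with a failed implant attempt into the DRCFR analysis. Sections 9.1 and 10.1 and the definition of an attempt in Table 25-2 have those subjects followed for about 30 days and then withdrawn.

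**The concern.** Whether a leaver is analysed depends on that leaver's outcome. A complication before leaving keeps the subject in the numerator of failures and in the denominator. A clean course removes the subject from the denominator. The failure proportion is therefore pushed up even if leaving has nothing to do with complications.

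For attempt-only subjects the asymmetry is built in. They are withdrawn at about 30 days, so they cannot reach the 3-month evaluation on the planned schedule and in effect can count only as failures.

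The inflation from 49 to 62 treats attrition as a plain loss of numbers and makes no allowance for this. The exact test is also coarse at this size, so one subject fewer can change the number of events allowed. At stake is a downward-biased primary safety estimate, and a device that performs as assumed failing its goal more often than the plan suggests.

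**Working it through.** **Inputs from the plan.** One-sided alpha 0.05, expected DRCFR 97.5% (complication risk 0.025), goal 87.5%, exact binomial, 80% power, 20% attrition (12.3, 12.1.1.2).

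**Assumptions not in the plan.** The 97.5% applies to all subjects. Leaving is unrelated to complications. A share f of leavers' complications is seen before they leave (f = 0, 0.5 or 1).

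**1. The plan's own figure.** Let c(n) be the largest number of failures for which P(X ≤ c | n, 0.125) ≤ 0.05.

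| Evaluable n | c(n) | Exact alpha | Power at 0.025 |
|---|---|---|---|
| 48 | 1 | 0.0129 | 66.2% |
| 49 | 2 | 0.0461 | 87.6% |
| 50 | 2 | 0.0418 | 87.1% |
| 59 | 2 | 0.0168 | 81.7% |
| 60 | 3 | 0.0482 | 93.7% |
| 62 | 3 | 0.0403 | 93.0% |

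The smallest n with at least 80% power is 49, and 49/0.8 = 61.25, rounded up to 62. Both figures match. At 49 the power attained is 87.6%, so there is slack above 80%; at 48 it is 66.2%.

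**2. Bias from the exclusion rule.** With attrition of 0.20:
- failures kept = 0.8 × 0.025 + 0.2 × 0.025 × f = 0.020 + 0.005f
- subjects kept = 1 − 0.2 × (1 − 0.025f) = 0.800 + 0.005f
- f = 0: 0.0200/0.8000 = 2.5%
- f = 0.5: 0.0225/0.8025 = 2.8%
- f = 1: 0.0250/0.8050 = 3.1%

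**3. Power with a fixed number of leavers L.** Failures are A + B, with A ~ Bin(62 − L, 0.025) and B ~ Bin(L, 0.025f). The analysed number is 62 − L + B. The endpoint is met if A + B ≤ c(62 − L + B).

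| Leavers | f = 0 | f = 0.5 | f = 1 |
|---|---|---|---|
| 12 (19.4%) | 87.1% | 83.5% | 79.8% |
| 13 (21.0%) | 87.6% | 83.8% | 79.8% |
| 14 (22.6%) | 66.2% | 65.7% | 64.3% |
| Lowest over 0–12 | 81.7% | 81.1% | 79.8% |

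The f = 1 entry at 12 leavers can be checked by hand. All complications among 62 subjects count, but the limit is the one for 50 or so, namely 2. P(Bin(62, 0.025) ≤ 2) = 0.2081 + 0.3308 + 0.2587 ≈ 0.798.

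**4. Power if 20% is a rate.** Let L ~ Bin(62, 0.20), with mean 12.4. Then P(L > 12) = 47% and P(L ≥ 14) = 35%. Averaging step 3 over L gives 79.7% (f = 0), 75.8% (f = 0.5) and 71.9% (f = 1). So random attrition alone takes power from about 87% to 79.7%, and the exclusion rule removes a further 4 to 8 points (79.7 − 75.8 = 3.9; 79.7 − 71.9 = 7.8).

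**5. The alternative analysis.** A product-limit estimate with a beta-product one-sided 95% lower bound was simulated under the same random 20% attrition. Complications were either spread evenly over 3 months or all at implant. Power was about 81–83% and type I error 1.2–2.3%. With no leavers this bound equals the planned exact binomial bound.

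**The case against.** The strongest reply is that the plan meets its own condition. Sections 12.1.1.2 and 12.3 and Table 12-1 all write attrition as a maximum, and within it at most 12 of 62 leave. The worst case there is 79.8%, because 49 evaluable subjects attain 87.6% rather than 80%. Any fixed-size design loses power once attrition passes what was planned. The rule also errs against the sponsor: it makes a good device likelier to fail, not a poor one likelier to pass. And if the 97.5% from prior devices was measured on an evaluable set built the same way, the rule costs no power. Power is then about 87% with 12 leavers, or 79.7% with random attrition.

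Most of this stands. A reader might infer that 80% power is simply not delivered at 20% attrition and that Table 12-1 should read 72–76%. The documents do not support that. Those figures need a random 20% loss per subject, with 14 or more lost in 35% of trials, and half to all of leavers' complications seen.

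Three things are not answered. The exclusion depends on outcome whatever the attrition. The synopsis gives 20% without calling it a ceiling. Nothing in the plan replaces lost subjects or otherwise holds losses to 12; enrolment closes at 62 (10.4).

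**Conclusion.** The sample size arithmetic is sound, and the 80% claim holds to within about 0.2 points while no more than 12 or 13 of 62 are lost. The defect is in the estimator. The exclusion rule raises the apparent complication rate from 2.5% to about 2.8–3.1% at 20% attrition, and attempt-only subjects can in effect enter only as failures. If 20% is an expected rate, power is about 72–80%. That fall has two causes: the outcome-dependent exclusion, and the drop from two allowed events to one at 48 evaluable.

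The bias range rests on half to all of leavers' complications being seen and on 97.5% applying to all subjects. The power range runs from none to all seen and also assumes independent leaving. The plan gives none of these.

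**What to change.** In 12.1.1.2 and 12.4.1, estimate the 3-month DRCFR by the product-limit method, censoring complication-free leavers, including attempt-only subjects, at last contact. Compare a beta-product one-sided 95% lower bound with 87.5%. Keep the present exact binomial analysis as a sensitivity analysis. Name one evaluation day for the estimate, since 12.1.1.2 runs to 91 + 21 days and 12.4.1 to 91 days.

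The cost is changed wording and a little more analysis work, with no extra subjects. The method assumes non-informative censoring, which should be stated.

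If the present rule is kept, leave the 80% in Table 12-1, but say there and in the synopsis that it applies only while at most 20% (12 of 62) are lost. Reaching 80% under the present rule with a random 20% rate would instead need 63, 68 or 74 enrolled, for none, half or all of leavers' complications seen.

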12.4. General Statistical Methods

12.4.1. Analysis Sets

All subjects where implant with the Ingenio 2 CRT-P device was successful will be included in the primary endpoints analyses. For the DRCFR primary endpoint, subjects where the Ingenio 2 CRT-P device was attempted but not successfully implanted will also be included. Nevertheless, for the DRCFR primary endpoint, subjects that die/withdraw or are lost-to-follow-up prior to the 3-month endpoint evaluation (91 days post-implant or post-implant attempt) and have not experienced device-related complication will be excluded from the analysis.

12.4.2. Descriptive Statistical Methods

Descriptive statistical methods will be used to summarize the data from this study, with hypothesis testing performed for the primary endpoints. Unless otherwise stated, all statistical testing will be one-sided and will be performed using a significance (alpha) level of 0.05.

Continuous variables as a minimum will be described by number of non-missing observations (n), arithmetic mean (Mean), SD, minimum (Minimum), median (Median), and maximum (Maximum). One additional decimal point for mean and median and 2 additional decimal points for SD will be used.

Categorical variables will be presented using the number of non-missing observations (n) or the number of subjects in the population (N) as applicable and percentages (%). Percentages will be rounded to one decimal place. Unless otherwise stated, two-sided 90% CIs will be provided when relevant. The two-sided 90% CI will be presented as it provides:

- the one-sided 95% lower limit when the upper bound is ignored to assess superiority.
- the one-sided 95% upper limit when the lower bound is ignored to assess superiority.

12.4.3. Number of Subjects per Investigative Site

Approximately 10 investigational centers will enroll 62 subjects. If a center does not enroll a subject within a 3-month time period, the site may be replaced at the discretion of the sponsor.

12.5. Data Analyses

12.5.1. Interim Analyses

No interim analyses are planned.

12.5.2. Subgroup Analyses

No subgroup analyses are planned due to the small number of subjects included in this evaluation.

12.5.3. Other Analyses

Descriptive statistics of subject demographic and baseline characteristics will be presented.

12.5.4. Changes to Planned Analyses

Any changes to the planned statistical analyses made prior to performing the primary endpoints analyses will be documented in an amended Statistical Analysis Plan approved prior to performing the analyses of primary endpoints. Changes from the planned statistical methods after performing the analyses of primary endpoints will be documented in the clinical study report along with a reason for the deviation.

13. Data Management

13.1. Data Collection, Processing, and Review

Subject data will be recorded in a limited access secure electronic data capture (EDC) system. The time periods for recording study data (enrollment, implant data, etc.) is specified in the site guidelines.

The clinical database will reside on a production server hosted by AptivAdvantage. All changes made to the clinical data will be captured in an electronic audit trail and available for review by BSC or its representative. The associated database has been designed to meet regulatory compliance for deployment as part of a validated system compliant with laws and regulations applicable to the conduct of clinical studies pertaining to the use of electronic records and signatures. Database backups are performed regularly.

The Investigator provides his/her electronic signature on the appropriate electronic Case Report Forms (eCRFs) in compliance with local regulations. A written signature on printouts of the eCRFs must also be provided if required by local regulation. Changes to data previously submitted to the sponsor require a new electronic signature by the Investigator acknowledging and approving the changes.

Visual and/or electronic data review will be performed to identify possible data discrepancies. Manual and/or automatic queries will be created in the EDC system and will be issued to the site for appropriate response. Site staff will be responsible for resolving all queries in the database.

All ECG readings should be uploaded to the study database for core lab review. Refer to the Core Lab Manual of Operations for more details.

13.2. Data Retention

The Investigator or Investigational site will maintain, at the investigative site, in original format all essential study documents and source documentation that support the data collected on the study subjects in compliance with International Conference on Harmonization (ICH)/GCP guidelines. Documents must be retained for at least 2 years after the formal discontinuation of the clinical investigation of the product. These documents will be retained for a longer period of time by agreement with BSC or in compliance with other local regulations. It is BSC's responsibility to inform the Investigator when these documents no longer need to be maintained. The Investigator will take measures to ensure that these essential documents are not accidentally damaged or destroyed. If for any reason the

Investigator withdraws responsibility for maintaining these essential documents, custody must be transferred to an individual who will assume responsibility and BSC must receive written notification of this custodial change.

13.3. Core Laboratories

All ECG readings should be uploaded to the study database for core lab review. Refer to the Core Lab Manual of Operations for more details.

14. Amendments

If a CIP revision is necessary which affects the rights, safety or welfare of the subject or scientific integrity of the data, an amendment is required. Appropriate approvals (e.g., EC) of the revised CIP must be obtained prior to implementation.

15. Deviations

An Investigator must not make any changes or deviate from this CIP, except to protect the life and physical well-being of a subject in an emergency. An Investigator shall notify the sponsor and the reviewing EC of any deviation from the investigational plan to protect the life or physical well-being of a subject in an emergency, and those deviations which affect the scientific integrity of the clinical investigation. Such notice shall be given as soon as possible, but no later than 5 working days after the emergency occurred, or per prevailing local requirements, if sooner than 5 working days.

All deviations from the investigational plan, with the reason for the deviation and the date of occurrence, must be documented and reported to the sponsor using on the EDC eCRF and a CIP Deviation Worksheet should also be completed and filed in the subject file. Sites may also be required to report deviations to the EC, per local guidelines and government regulations.

Deviations will be reviewed and evaluated on an ongoing basis and, as necessary, appropriate corrective and preventive actions (including notification, center re-training, or discontinuation) will be put into place by the sponsor.

16. Compliance

16.1. Statement of Compliance

This study will be conducted in accordance with ISO 14155 (Clinical Investigation of Medical Devices for Human Subjects - Good Clinical Practice), the relevant parts of the ICH Guidelines for Good Clinical Practices, ethical principles that have their origins in the Declaration of Helsinki, and pertinent individual country laws and regulations. The study shall not begin until the required approval/favorable opinion from the EC and/or regulatory authority has been obtained, if appropriate. Any additional requirements imposed by the EC or regulatory authority shall be followed, if appropriate.

16.2. Investigator Responsibilities

The Principal Investigator of an investigational center is responsible for ensuring that the study is conducted in accordance with the Clinical Study Agreement, the CIP/protocol, ISO 14155, ethical principles that have their origins in the Declaration of Helsinki, any conditions of approval imposed by the reviewing EC, and prevailing local and/or country laws and/or regulations, whichever affords the greater protection to the subject.

The Principal Investigator's responsibilities include, but are not limited to, the following:

- prior to beginning the study, sign the Investigator Agreement and CIP Signature page documenting his/her agreement to conduct the study in accordance with the CIP.
- provide his/her qualifications and experience to assume responsibility for the proper conduct of the study and that of key members of the center team through up-to-date curriculum vitae or other relevant documentation and disclose potential conflicts of interest, including financial, that may interfere with the conduct of the clinical study or interpretation of results.
- make no changes in or deviate from this CIP, except to protect the life and physical well-being of a subject in an emergency; document and explain any deviation from the approved CIP that occurred during the course of the clinical investigation.
- create and maintain source documents throughout the clinical study and ensure their availability with direct access during monitoring visits or audits; ensure that all clinical-investigation-related records are retained per requirements.
- ensure the accuracy, completeness, legibility, and timeliness of the data reported to the sponsor in the eCRFs and in all required reports.
- record, report, and assess (seriousness and relationship to the device/procedure) every observed DD.
- report to BSC, per the CIP requirements, all USADEs, SADEs, ADEs, DDs; all SAEs; documentation of freedom from UADEs and device-related malfunctions.
- report to the EC and regulatory authorities any SAEs and DDs that could have led to a SADE, if required by the national regulations or this CIP or by the EC, and supply BSC with any additional requested information related to the safety reporting of a particular event.
- allow the sponsor to perform monitoring and auditing activities, and be accessible to the monitor and respond to questions during monitoring visits.
- allow and support regulatory authorities and the EC when performing auditing activities.
- ensure that informed consent is obtained in accordance with this CIP and local EC requirements.
- provide adequate medical care to a subject during and after a subject's participation in a clinical study in the case of a device event, as described in the ICF.

- inform the subject of the nature and possible cause of any device events experienced.
- inform the subject of any new significant findings occurring during the clinical investigation, including the need for additional medical care that may be required.
- provide the subject with well-defined procedures for possible emergency situations related to the clinical study, and make the necessary arrangements for emergency treatment.
- ensure that clinical medical records are clearly marked to indicate that the subject is enrolled in this clinical study.
- ensure that, if appropriate, subjects enrolled in the clinical investigation are provided with some means of showing their participation in the clinical investigation, together with identification and compliance information for concomitant treatment measures (contact address and telephone numbers shall be provided).
- inform, with the subject's approval or when required by national regulations, the subject's personal physician about the subject's participation in the clinical investigation.
- make all reasonable efforts to ascertain the reason(s) for a subject's premature withdrawal from clinical investigation while fully respecting the subject's rights.
- ensure that an adequate investigation site team and facilities exist and are maintained and documented during the clinical investigation.
- ensure that maintenance and calibration of the equipment relevant for the assessment of the clinical investigation is appropriately performed and documented, where applicable.

